7.10 Safety Evaluation

All device-related, therapy-related, and procedure-related adverse events (AE) and device deficiencies (DD) from the Device Trial Start Visit until study exit will be characterized in all subjects who started trialing and in all subjects who were implanted.

AEs and DDs will be coded and summarized overall and by location of pain using the most recent version of Medical Dictionary and Regulatory Affairs (MedDRA).

The AEs will also be categorized by relationship to study device and/or therapy. AEs will be presented in summary tables displaying the number of serious events, the number of events, and the number and percentage of subjects with one or more events. A summary of all device or therapy related AEs and of any deaths will also be provided. A narrative of each serious device- or therapy-related AEs will be provided.

DDs will be presented in summary tables displaying the number of deficiencies, and the number and percentage of subjects with deficiencies.

Device exposure will be summarized in those that started trialing from the ACS and the FAS and is considered from the time the subject is first exposed to the neurostimulation system (at the beginning of the device trial) until the product is explanted, or the subject discontinues from or completes the study, if later. Amount of exposure will be summarized (in months) using descriptive statistics such as mean, standard deviation, minimum, and maximum.

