Safety Assessments	The following Adverse Events will be collected: device-related, procedure-related, therapy-related, and serious. All device deficiencies will be collected.

Evaluation of Long-term Patient Experience with a Medtronic Closed-Loop SCS System (Closed-Loop SCS study)

Clinical Investigation Plan

06JAN2023

Version 4.0

Page 18 of 117

Medtronic

Statistics

For the primary objective, it is hypothesized that the proportion of low-back and/or leg pain subjects (p) having a reduction in overstimulation sensation during Neuro Sense On compared to Neuro Sense Off period exceeds a performance goal of 50%.

$$H_0: p \leq 50\%$$

$$H_A: p > 50\%$$

The proportion of low-back and/or leg pain subjects with a reduction in overstimulation sensation during Neuro Sense On compared to Neuro Sense Off period will be calculated, with a one-sided 97.5% confidence lower bound. This proportion will be tested against 50% using a binomial exact test. The confidence lower bound needs to be greater than 50%, or equivalently, the p-value must be less than 0.025 to reject the null hypothesis.

For the primary objective, PASS 2020 Tests for One Proportion was used to calculate the sample size, with a null proportion of 50%, and an alternative proportion of 80%; 28 subjects are needed to achieve more than 90% power with a one-sided test and $\alpha = 0.025$. This is a subset of the total device implanted low-back and/or leg pain subjects.

[figure not shown]

The first secondary objective is to characterize the overall responder rate, which is defined as the percentage of low-back and/or leg pain implanted subjects who experience at least a 50% improvement in overall pain, as measured by the VAS, from Baseline to the 3-Month Visit.

The other secondary objective is to characterize the responder rate separately for low-back or leg pain, as

measured by the pain-specific VAS, from Baseline to the 3-Month Visit. The low-back responder rate will be characterized for subjects with baseline back VAS \geq 60 mm, and the leg responder rate will be characterized for subjects with baseline leg VAS \geq 60 mm.

Up to 45 implanted subjects with low-back and/or leg pain are desired to characterize the responder rates at the 3-Month Visit. The proportion of responders will be presented for both secondary objectives, with 95% confidence intervals. Information from subjects with data available at baseline and the 3-Month Visit will be used for these objectives.

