10.6 Enrollment

A subject is considered enrolled when the subject and the Principal Investigator or authorized designee, impartial witness, as required, have personally signed and dated the informed consent. The date the subject signed the informed consent form, as required by law, must be documented in the subject's

medical records. A log of all subjects enrolled in the study should be maintained. Enrollment can be a stand-alone visit or can occur on the same day as screening. Once consent is obtained, report adverse events/deaths, study deviations and subject exits as they occur. No study-related procedures or testing may be conducted prior to completion of the informed consent process with a subject.

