10.22 Assessment of Safety

To characterize all device-related, therapy-related, and procedure-related adverse events and device deficiencies. Adverse events and device deficiencies will be summarized using summary tables displaying the frequency and percentages, by study phase, and in total. Adverse events will be summarized by seriousness as well.

See Section 12 for further information on the collection of AEs and safety information.

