12.1 Adverse Events

AE definitions are provided in Table 7. The following AEs will be collected throughout the study duration, starting at the time of signing the IC:

- procedure related
- device related
- therapy related
- serious adverse events regardless of relatedness

Reporting of these events to Medtronic will occur on an AE eCRF. Each event must be reported separately. Documented pre-existing conditions are not considered AEs unless the nature or severity of the condition has worsened. A subset of AEs will be collected in this study as these are the most relevant to the study device and study design given no new or increased risk with the Inceptiv system.

UAE, listed in Table 7, need not be reported unless the adverse event worsens or is present outside the stated timeframe post-implant.

For AEs that require immediate reporting (see Table 9), initial reporting may be done by phone, fax, or on the eCRF completing as much information as possible. The completed AE CRF must be submitted to Medtronic as soon as possible.

Any medication/treatment associated with the treatment of an AE must be reported

Subject deaths are also required to be reported. Refer to Section 12.6 for Subject Death collection and reporting requirements.

Events that are not reportable for this study are:

- Sensation of stimulation (paresthesia)
 - Sensation of stimulation (e.g., tingling, buzzing) will not be reported as this may occur as part of this therapy.
 - Sensation of stimulation brought by protocol-prescribed activities (i.e. coughing, laughing, Valsalva) if transient and reversed by the subject returning to a neutral position (anytime occurred).
 - Overstimulation: uncomfortable sensation of stimulation (intense tingling, shocking, jolting) brought by protocol-prescribed activities if transient and reversed by the subject returning to a neutral position (as defined in Section 14.4).

- Transient periods of sensation or stimulation events that are uncomfortable to the subject that do not result in an intervention or are relieved by change in body position or decreasing therapy intensity

NOTE: Extended periods of sensation or overstimulation events that are uncomfortable to the subject (e.g. tingling, shocking, jolting) that result in intervention (e.g. reprogramming, turning the device off) will be reported.

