14.7 Safety Assessment

To characterize all device-related, therapy-related, and procedure-related adverse events and device deficiencies from the start of the device trial until study exit. Adverse events and device deficiencies will be summarized using summary tables displaying the frequency and percentages of events as well as the number of subjects experiencing events, by study phase, and in total. Adverse events will be summarized by seriousness as well.

[REDACTED]

[REDACTED]

[REDACTED]

[REDACTED]

[REDACTED]	[REDACTED]	[REDACTED]	[REDACTED]	[REDACTED]
[REDACTED]	[REDACTED]	[REDACTED]	[REDACTED]	[REDACTED]
[REDACTED]	[REDACTED]	[REDACTED]	[REDACTED]	[REDACTED]
[REDACTED]	[REDACTED]	[REDACTED]	[REDACTED]	[REDACTED]
[REDACTED]	[REDACTED]	[REDACTED]	[REDACTED]	[REDACTED]
[REDACTED]	[REDACTED]	[REDACTED]	[REDACTED]	[REDACTED]
[REDACTED]	[REDACTED]	[REDACTED]	[REDACTED]	[REDACTED]
[REDACTED]	[REDACTED]	[REDACTED]	[REDACTED]	[REDACTED]
[REDACTED]	[REDACTED]	[REDACTED]	[REDACTED]	[REDACTED]
[REDACTED]	[REDACTED]	[REDACTED]	[REDACTED]	[REDACTED]

For the primary objective, a subset (28) of the total device implanted low-back and/or leg pain subjects are needed to evaluate the endpoint. For the secondary objectives, up to 45 implanted subjects with low-back and/or leg pain are desired to characterize the responder rates at the 3-Month Visit. Up to 9 implanted subjects with upper limb and/or neck pain are desired to characterize the population at the 3-Month Visit.

[REDACTED]

[REDACTED]

[REDACTED]

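### All SAEs are collected from consent, but the safety scope sentences name only related events from the device trial onward, so it is unclear whether unrelated or pre-trial SAEs will be tabulated

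*SAP*

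**What the plan says.** **Collection.** Protocol 12.1 states: "The following AEs will be collected throughout the study duration, starting at the time of signing the IC". Its list has procedure-, device- and therapy-related events and, as a fourth category, "serious adverse events regardless of relatedness". The synopsis agrees: "The following Adverse Events will be collected: device-related, procedure-related, therapy-related, and serious". Protocol 10.6 adds: "Once consent is obtained, report adverse events/deaths, study deviations and subject exits as they occur".

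**Analysis.** The opening sentence of SAP 7.10 takes device-, therapy- and procedure-related AEs and device deficiencies. It says that these "from the Device Trial Start Visit until study exit will be characterized in all subjects who started trialing" and in all subjects who were implanted. Protocol 14.7 names the same three kinds of related event plus deficiencies, "from the start of the device trial until study exit". Protocol 10.22 has the same aim, "To characterize all device-related, therapy-related, and procedure-related adverse events and device deficiencies", but no start point.

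**Other sentences.** SAP 7.10 goes on to categorise AEs by relationship to device and/or therapy. It promises tables with counts of serious events and of all events, summarizes device- or therapy-related AEs and any deaths, and gives narratives for serious device- or therapy-related events. The synopsis and Protocol 10.22 and 14.7 each say that AEs will also be summarized by seriousness.

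**The concern.** The data collected are wider than the scope stated for reporting them. An all-SAE table lets a reader see serious events that may have been wrongly judged unrelated. If the table holds only related events, the reported serious-event count depends on the judgement that it should help to check.

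That matters more here than in a late-phase trial of a known device. SAP section 3 calls this a first-in-man study. Protocol 13.2 provides no data monitoring committee. Under Protocol 12.5.1 (Table 8) relatedness is classified by the investigator and the sponsor, and Protocol 10.15.3 leaves sponsor personnel unblinded to the randomization assignments.

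The start point also differs within the Protocol, because 14.7 has one and 10.22 does not. The version history entry for version 2.0 gives a reason for having no such limit in 10.22: a deficiency may arise before the device is used. I cite the entry only for that reason, which applies equally to the current text of 14.7 and SAP 7.10.

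**Working it through.** No stated figure has to be reproduced. The check is to take each kind of collected event and ask where the current text puts it. In the narrow reading, the scope sentences of Protocol 14.7 and SAP 7.10 govern everything after them. In the wide reading, the later table sentences of SAP 7.10 and the synopsis stand on their own.

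| Collected event | Narrow reading | Wide reading |
|---|---|---|
| SAE, related, after device trial start | Tabulated | Tabulated |
| SAE, non-fatal, not related, after device trial start | Outside scope | Tabulated |
| SAE, non-fatal, between consent and trial start, subject later trialed | Outside scope (window) | Unclear: the SAP table sentence gives no window, the scope sentence does |
| SAE, non-fatal, subject never trialed | Outside both SAP 7.10 populations | Covered only by the general synopsis wording |
| Device deficiency before trial start | Outside scope (window) | Within Protocol 10.22 and the synopsis |
| Death | Summarized, no relatedness limit | Summarized |

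Only the first and last rows come out the same under both readings. Narratives do not fill the gap, because they are limited to serious events related to device or therapy.

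**Reach, from the documents' own figures**

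- Implanted subjects (Protocol 6 and 10.8): up to 57 + 12 = 69, each followed for up to 24 months after activation. An SAE judged not related could occur at any time in that period.
- Enrolled but not implanted: up to 140 − 69 = 71, and 71 / 140 = 51%. The visible text does not say how many of these never start a device trial. Between 0 and 71 consented subjects could therefore fall outside both SAP 7.10 populations.
- SAP section 5 has lower figures (90 enrolled, 50 + 10 = 60 implanted), which would make that range 0 to 30.
- Pre-trial window: up to 28 days from Enrollment/Baseline (Protocol 10.3, Table 6). The synopsis counts the 28 days from the baseline assessment, and Protocol 10.6 lets enrollment be a stand-alone visit. The time from consent to trial may therefore exceed 28 days.
- SAE rate: not given, so no expected number of affected events can be calculated.

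**The case against.** **The text can be read more widely.** Only the opening sentence of SAP 7.10 carries the limits. Its table sentence counts serious events without repeating them. Categorising by relationship makes more sense if unrelated events are present. The separate summary of device- or therapy-related AEs suggests that the main tables hold more, although procedure-related events alone could explain that. A programmer who tabulated every collected SAE could claim to follow the plan. This stands. A reader might infer that the safety tables definitely exclude unrelated SAEs, and the documents do not support that. The supportable point is that the scope is ambiguous.

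**There are other safeguards.** Under Protocol 12.4 (Table 7), events whose relatedness cannot be assessed are classed as possible. Under 12.5.1, possible, probable and causal all count as related. Only events actively judged not related are at issue. Investigators send all SAEs to the sponsor (12.5.2), sponsor personnel including the Medical Advisor meet regularly to review AEs (13.2), and safety reports go to investigators and ethics committees at least annually (16.8.2). This also stands. A reader might infer that harm would go undetected during the trial, and the documents do not support that either. The gap is in the planned summaries, and these safeguards do not replace a final table.

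**The pre-trial part is small.** Before the device trial there are only consent, psychological evaluation, imaging and baseline assessments. Relatedness is defined by the system, its therapy and its procedures, so an SAE in that window would almost always be not related and largely repeats the main point. Starting device-safety tables at first exposure is also reasonable, and it matches the SAP's own definition of exposure. For AEs this mostly stands, which is why a listing is enough. Multiplying enrolled subjects by 28 days would give unexposed time. It would be neither an event count nor a firm upper limit.

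**Conclusion.** The point holds as a conflict between what is collected and what the scope sentences say will be summarized, with an ambiguity that the rest of the text does not settle. Read as governing, Protocol 14.7 and SAP 7.10 leave out non-fatal SAEs judged not related at any time, and SAEs and device deficiencies before the device trial. Read more loosely, they may include them. Deaths are covered either way.

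The ambiguity is itself a defect, because the reported SAE count then depends on who programs the table. The stronger part is unrelated SAEs after trial start; the pre-trial part adds little for AEs and somewhat more for deficiencies.

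The number of events affected is unknown. The conclusion rests on the visible text of SAP 7.10 and the Protocol sections cited, and assumes that no redacted passage defines a separate all-SAE table. Primary and secondary estimates, the hypothesis test and expedited reporting are unaffected. It is a low-cost clarification worth making before the tables are programmed.

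**What to change.** 1. In Protocol 14.7 and SAP 7.10, state that all collected SAEs are summarized regardless of relatedness.
2. Add one SAE table by relatedness (related, not related) and by period (consent to device trial start, device trial, implant onward), using the SAP's All Consented Set so that subjects who never trial are included.
3. Add a listing of events and device deficiencies between consent and device trial start in the same set.
4. Keep the existing related-event tables from trial start in trialed and implanted subjects. They remain the right view of device safety after exposure.
5. Align Protocol 10.22 and the synopsis with the new scope and start point.

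The cost is a wording change, one table and one listing from data already collected. The reported SAE count may be higher than under the narrow reading. By how much cannot be said without an SAE rate.

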		
 ▪ Clinician Tablet ▪ Clinician Programmer Application ▪ Stimulation Trialing Clinician Programmer Application ▪ Programmer Platform Software-Communication Manager Application ▪ Patient Data Service Application ▪ Patient Handset ▪ Patient Programmer Application ▪ Patient Programmer Trialing Application ▪ Patient Telemetry Communicator ▪ Recharger Application ▪ Recharger 
 ○ Procedure ○ Therapy
Expectedness	Sponsor	USADE
Seriousness	Investigator	SAE, device deficiencies with SADE potential
	Sponsor	SAE, device deficiencies with SADE potential
Diagnosis	Investigator	Based on presenting signs and symptoms and other supporting data
	Sponsor	MedDRA term assigned based on the data provided by Investigator

*Adverse events that are classified as having a relationship of possible, probable or causal to the investigational device or procedure or therapy are considered to be related to the investigational medical device and are classified as ADEs.

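### SAP 7.10 puts procedure-related adverse events in scope but leaves them out of its relatedness split, related-event summary and narratives, and omits the by-phase tables the protocol requires

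*SAP*

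**What the plan says.** The scope sentence of SAP 7.10 begins "All device-related, therapy-related, and procedure-related adverse events (AE) and device deficiencies (DD" and covers the period from the start of the device trial to study exit, both in subjects who started trialing and in subjects who were implanted. The outputs that follow are:

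- Tabulation: "AEs and DDs will be coded and summarized overall and by location of pain".
- Counts: "AEs will be presented in summary tables displaying the number of serious events, the number of events", together with the number and percentage of subjects affected.
- Relatedness split: "The AEs will also be categorized by relationship to study device and/or therapy".
- Related-event summary: "A summary of all device or therapy related AEs and of any deaths will also be provided".
- Narratives: "A narrative of each serious device- or therapy-related AEs will be provided".

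The protocol has three relatedness classes. Table 7 (Section 12.4) defines procedure-related separately from device-related and therapy-related; it covers procedures for the trial, implant, explant and surgical modification of the system. Table 8 (Section 12.5.1) has investigator and sponsor classify the relationship to device, procedure and therapy. A footnote to Table 8 adds that events at least possibly related to the investigational "device or procedure or therapy are considered to be related to the investigational medical device", and so count as adverse device effects (ADEs). Protocol 14.7 names all three classes in its safety aim. Both 10.22 and 14.7 call for adverse event and device deficiency tables "by study phase, and in total".

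**The concern.** The SAP announces three classes and specifies output for two. A programmer who works from the output sentences would produce no procedure-related category, and would have no clear instruction on whether a serious event related only to a procedure needs a narrative. Two programmers could handle the same event differently and both claim to have followed the plan.

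This matters because the SAP's Introduction calls the study first-in-man for the fully implantable device, and subjects who complete the sequence undergo trial lead placement, lead explant and permanent implant. Protocol 13.2 has no data monitoring committee; sponsor personnel review safety. A reader of the report will want to tell harm from the operations apart from harm from the device or the stimulation, and to see when in the sequence it occurred.

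**Working it through.** No arithmetic applies, and there is no planned figure to reproduce. The check compares the texts and then follows an event through the SAP under each available reading.

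**Step 1. Item by item.**

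| Item | Protocol | SAP 7.10 |
|---|---|---|
| Scope | Device, therapy, procedure (14.7) | Device, therapy, procedure |
| Relatedness classes | Three, defined separately (Table 7) and classified separately (Table 8) | Split names device and therapy |
| Summary of related events | Not specified in the visible safety text | Device or therapy, plus deaths |
| Narratives of serious related events | Not specified in the visible safety text | Device or therapy |
| Breakdown of tables | By study phase and in total (10.22, 14.7) | Overall and by pain location |

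Procedure-related appears once in SAP 7.10, in the scope sentence, and in none of the three relatedness outputs. Study phase does not appear there at all. The text of 7.10 carries no redaction marks, so neither gap comes from blacked-out text.

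**Step 2. What happens to a serious, non-fatal event.** Reading A takes the Table 7 classes as they stand. Reading B applies the Table 8 footnote.

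| Event related to | Narrative, A | Narrative, B | Procedure subtotal, A or B |
|---|---|---|---|
| Device only | Yes | Yes | Not applicable |
| Therapy only | Yes | Yes | Not applicable |
| Device and procedure | Yes | Yes | None |
| Procedure only | Not called for | Yes, as device-related | None |

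The readings differ on narratives only in the last row. Under both, procedure-related events have no subtotal. Under B they are also merged into the device-related count, so that count means different things under A and B.

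**Step 3. Which reading the SAP intends.** It does not cite the footnote. The footnote folds therapy-related events into device-related as well. If it governed 7.10, naming therapy next to device would be redundant. That leans towards A but does not settle it, because the SAP states in its Introduction that it is based on the protocol.

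**Step 4. Whether the two populations supply the phase split.** They do not. Events are counted from the start of the device trial in both populations, so an implanted subject's trial-phase events sit alongside that subject's later events. Subtracting the implanted set from the trialed set isolates subjects who were never implanted, not the trial phase.

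**The case against.** The strongest reply is that little is lost. SAP 7.10 commits to characterising procedure-related events, codes all events in MedDRA, counts the serious ones and summarises any death. A coded table would normally show an infection or a haematoma under its own term. The footnote is a prespecified rule in the parent document, and applying it would bring serious procedure-related events into the narratives. Protocol Section 14 presents the SAP as added detail, so the SAP's silence does not cancel the by-phase commitment. The protocol's visible safety text promises neither narratives nor tables by relatedness.

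Most of this stands, and it limits the point. It does not supply a procedure-related subtotal under either reading, and it does not say whether the footnote governs. On narratives and relatedness tables, the gap is against the SAP's own scope sentence and the protocol's three-way classification. On study phase, it is a direct departure from protocol 10.22 and 14.7.

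Three stronger readings are tempting and should be resisted:

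- A reader might infer that serious surgical complications go unreported. They do not; they remain in the overall tables and counts.
- A reader might infer that trial-phase events cannot be separated from those after implant. The date of each reportable event is a required item (protocol 12.5), so phase can be derived; the SAP simply does not specify the table.
- A reader might infer that procedural risks are the main serious risks. The protocol lists such events in 11.2.1 and Appendix A without a visible rate; the earlier-study rates in Appendix A are blacked out. Some events could also carry both a device and a procedure label, since Table 7 counts events arising from the device's presence as device-related.

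**Conclusion.** The point holds as a gap in the safety specification. All three relatedness outputs in SAP 7.10 omit procedure, although the section's scope sentence includes it. The by-phase tables stated twice in the protocol are absent. The consequence is definite for the subtotal, since none is specified, and conditional for narratives: a serious, procedure-only event gets one if the Table 8 footnote is applied and is not assigned one if the Table 7 classes are used as they stand.

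The number of events affected cannot be stated from the documents. No data collection, hypothesis test or efficacy endpoint is touched. This conclusion assumes that SAP 7.10 as shown is the complete safety analysis text. It should be corrected before the final analysis, because it changes what the safety report shows and costs little.

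**What to change.** In SAP 7.10:

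1. Categorise adverse events by relationship to device, procedure and therapy, using the Table 7 definitions, and state that an event with more than one relationship is counted under each.
2. Name device, procedure and therapy in both the related-event summary sentence and the serious-event narrative sentence.
3. If the Table 8 footnote is used, show the resulting ADE total as a separate, labelled roll-up and cite the footnote.
4. Add the adverse event and device deficiency tables by study phase, and in total, that protocol 10.22 and 14.7 require. Define the phase boundaries from visit or procedure dates.

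The cost is a SAP wording change, a few more table columns and possibly a few more narratives. No new data are needed: relatedness is on the adverse event eCRF (protocol 10.23), the procedure relationship is already classified (Table 8), and event dates are already required (12.5).

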Trial Lead Explant: Leads will be explanted at the end of the trial period. Self-reported pain relief will be collected. Subjects who have a 50% or greater reduction in pain will go onto a permanent SCS system implant in the study.

SCS Implant: An Inceptiv device will be implanted and connected to the lead(s).

Device Activation: The device will be turned on and the optimization period will begin.

[REDACTED]

Randomization and In-clinic Testing: Approximately 1-Month post Device Activation, subjects will undergo randomization and in-clinic testing. Subjects will be randomized to one of the two sequences: Neuro Sense On followed by Neuro Sense Off or Neuro Sense Off followed by Neuro Sense On. Subjects will be blinded to the settings tested. In each setting, subjects will perform a series of 3-5 activities [REDACTED] which are designed to induce overstimulation.

[REDACTED]

Subjects will be asked to rate the intensity of the overstimulation sensation they experienced while

[REDACTED]

[REDACTED]

Evaluation of Long-term Patient Experience with a Medtronic Closed-Loop SCS System (Closed-Loop SCS study)

Clinical Investigation Plan

06JAN2023

Version 4.0

Page 17 of 117

Medtronic

	
performing the activity using a 5-point Likert scale after each activity. Subjects will be asked which setting they preferred following the testing of both settings.
 
It is strongly recommended to program the SCS device with Neuro Sense On for the duration of the study.
 
Visits (3-, 6-, 12-, 18-, and 24-Months post Device Activation): Following in-clinic testing, subjects will come in for regular visits and efficacy and safety of the therapy will be assessed. Unscheduled visits may occur as necessary.
 
Phone Calls: Subjects will be called every week starting after Device Activation through the 3-Month Visit and monthly thereafter with an exception for the weeks or months when the subject has a study required visit. If the subject reports being Unsatisfied with the therapy, as determined by the phone call, the subject may be brought in for an Unscheduled visit for further therapy optimization. Alternatively, if the pain score reported by the subject during the phone call is ≥ 4, or if they report experiencing overstimulation the site should contact Sponsor Representative to further evaluate the need for therapy optimization; the Sponsor representative may contact the subject to troubleshoot over the phone prior to scheduling an in-clinic visit.

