10.3 Scheduled Visit Windows

Medtronic will provide the target dates and windows for each visit to the study site, as applicable. Should a subject miss a visit or the visit fall outside the pre-specified window, a study deviation must be reported and the original visit schedule maintained for subsequent visits. A late visit is preferred over a missed visit but must be accompanied by a study deviation. Visit windows are listed in Table 6.

Table 6: Data collection and study procedure requirements at subject visits

Visit	Visit ranges
Enrollment/Baseline	Not applicable
Device Trial	≤ 28 days after Enrollment/Baseline
Device Trial Phone Calls	Daily, as needed
Device Trial Lead Explant	≤ 10 days from Device Trial
SCS Implant	≤ 60 days after end of Device Trial
Phone Calls	Weekly starting after Device Activation through the 3-Month Visit and monthly thereafter with an exception for the weeks or months when the subject has a study required visit.
Device Activation (Day 0)	9-16 days after implant: pending wound healing
[REDACTED]	[REDACTED]
Randomization and In-clinic Testing	30 days ± 5 days from Day 0 (visit may occur on the same day as Visit 4 if Visit 4 is occurring within window, and at the discretion of the PI)
3-Month	90 days ± 15 days from Day 0
6-Month	180 days ± 15 days from Day 0
12-Month	360 days ± 30 days from Day 0
18-Month	540 days ± 30 days from Day 0

Visit	Visit ranges
24-Month	720 days \pm 30 days from Day 0

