10.11 Device Trial Lead Explant

All subjects will have their device interrogated. All reports (final) will be collected and leads will be explanted. Trial lead explant must occur on or before 10 days from the trial implant. Subjects who have 50% or greater reduction in pain will go onto a permanent INS implant in the study. If not, exit the subject from the study.

The following information is required to be collected at the trial lead explant visit:

- [REDACTED]
- Collect data files via the clinician programmer tablet and securely send to Medtronic
- Pain medication changes
- AEs/device deficiencies

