7.1.3 Analysis Sets

- The **All Consented Set** (ACS) will include all subjects who signed the study specific ICF and enrolled in the study.
- The **Full Analysis Set** (FAS) will include all device-implanted subjects.
- The **Primary Analysis Set** (PAS) will follow the intent-to-treat (ITT) principle to include randomized low-back and leg pain subjects who will be used for the primary objective, i.e., the first 28 randomized low-back and leg pain subjects.
- The **Complete Case Set** (CCS) will include all device-implanted subjects who have data available at baseline and follow-up. This set is defined for each outcome measure at each follow-up visit. [REDACTED]

[REDACTED]

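### SAP 7.10 runs device exposure straight through the interval between trial lead removal and Inceptiv implant, so exposure in the FAS can include up to 60 in-window days with no device in the body.

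*SAP*

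**What the plan says.** SAP 7.10 gives one definition for two populations: "Device exposure will be summarized in those that started trialing from the ACS and the FAS". The FAS is the set of subjects who received the implant (SAP 7.1.3). The clock starts "from the time the subject is first exposed to the neurostimulation system (at the beginning of the device trial") and runs "until the product is explanted, or the subject discontinues from or completes the study, if later". Nothing in the section removes any time in between or reports the phases separately. The result is summarised in months as mean, standard deviation, minimum and maximum.

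The protocol describes what happens in between:

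- The synopsis, on trial lead explant: "Leads will be explanted at the end of the trial period".
- Section 10.11: "Trial lead explant must occur on or before 10 days from the trial implant". Table 6 in Section 10.3 gives the same limit, "≤ 10 days from Device Trial".
- Table 6, on the SCS implant: "≤ 60 days after end of Device Trial".
- Table 6 then puts activation (Day 0) 9 to 16 days after implant and counts all follow-up visits from Day 0.

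**The concern.** A subject in the FAS passes through three periods before activation: a short trial on temporary leads and an external stimulator, an interval after those leads are removed, and the period after implant. In the middle period nothing is implanted and nothing is attached, so those days are not device exposure on any reading of the term. The SAP's single interval counts them all the same.

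The "if later" clause means that removal of the trial leads does not stop the clock. Even if those leads were taken to be the explanted product, exposure would still run on to study exit.

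What is at stake is the accuracy of a reported safety figure. SAP Section 3 calls this a first-in-man study of the fully implantable device, so a reader will look to the exposure summary to learn how long subjects carried it. As defined, the summary errs in one direction only, and its relative error is largest for subjects who leave early.

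**Working it through.** The documents state no exposure figure, so there is none to reproduce. The check builds exposure from the visit windows.

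**Inputs (Protocol Table 6)**

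- Trial length, T: at most 10 days
- End of trial to implant, G: at most 60 days
- Implant to activation, A: 9 to 16 days (16 used below)
- Last visit or exit, counted from Day 0, E: 720 days for a completer; 90 days for a subject taken to leave at the 3-month target

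**Formulas**

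- Exposure as SAP 7.10 counts it = T + G + A + E
- Time with any device in place = T + A + E
- Time with the Inceptiv implant = A + E
- Relative surplus = (counted − in place) / in place

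**At the window limits**

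| | Completer, E = 720 | Leaves at E = 90 |
|---|---|---|
| Counted | 10 + 60 + 16 + 720 = 806 | 10 + 60 + 16 + 90 = 176 |
| Any device in place | 10 + 16 + 720 = 746 | 10 + 16 + 90 = 116 |
| Surplus | 60 days, 60/746 = 8.0% | 60 days, 60/116 = 51.7% |
| Implant only | 16 + 720 = 736 | 16 + 90 = 106 |
| Surplus against implant only | 70 days, 70/736 = 9.5% | 70 days, 70/106 = 66.0% |

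In the SAP's unit, 60 days is 60 / (365.25/12) = 2.0 months. Activation at 9 days instead of 16 barely moves the completer figure: 799 counted against 739 in place, 60/739 = 8.1%.

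**Shorter gaps.** The documents give no distribution of actual gaps. As an assumption, keep T = 10 and A = 16 and vary G:

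- G = 15: 15/746 = 2.0% for the completer, 15/116 = 12.9% for the early leaver
- G = 30: 30/746 = 4.0% and 30/116 = 25.9%
- G = 60: 8.0% and 51.7%, as above

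Sixty days is a limit only for visits in window. Protocol 10.3 accepts late visits as deviations, so a single subject could exceed it.

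**The case against.** The strongest reply is that the SAP defines exposure to the neurostimulation system, not to the implant, and says openly that it begins at the trial. A reader might infer that the whole 70 days from trial start to implant is overstatement. The documents do not support that. The trial leads and external stimulator are market-released, but Protocol Table 3 lists the two trialing applications, the clinician tablet and the patient handset as investigational, and Table 7 counts them among the investigational components of the Inceptiv system. Trial days can therefore count as exposure to the system. Seventy days is the surplus only if time with the implanted Inceptiv is what is wanted.

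A reader might also infer that adverse event rates are diluted. SAP 7.10 plans numbers of events and numbers and percentages of subjects, and the protocol plans frequencies and percentages. No visible passage divides events by exposure time. Nor does any passage name the exposure summary as the measure of how long the implant was observed; that is a use a reader may make of it, not one the SAP states.

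A third reply is that the clock agrees with the adverse event window, which also opens at the device trial, including for implanted subjects. This stands, and it limits the remedy. Starting FAS exposure at implant while still counting trial and gap events would inflate any rate built from the two. Protocol 10.22 and 14.7 already require events to be summarised by study phase, so trial-phase events can be separated.

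None of these replies covers the gap itself. Between trial lead removal and implant there is no system in or on the subject.

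**Conclusion.** The point holds for the gap. Followed as written, SAP 7.10 counts up to 60 in-window device-free days as device exposure for every implanted subject. That is about 8% for a subject followed to Day 720 and about 52% for one leaving at Day 90. Both figures assume a 10-day trial, a 60-day gap and activation 16 days after implant. Typical values may be well below these limits.

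The consequence is confined to the descriptive exposure summary. The primary analysis, the responder rates and the planned adverse event percentages do not depend on it. The rule for when exposure ends is a separate matter, not judged here.

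**What to change.** In SAP 7.10, replace the single interval with two:

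1. Trial-system exposure, from trial lead placement to trial lead explant, for all subjects who started the trial.
2. Implant exposure for the FAS, starting on the day of Inceptiv implant.

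If a total is reported, add the two and leave out the interval between them. Keep the adverse event window as it stands. State that if any event rate per exposure time is computed, events and exposure must come from the same phase, trial or post-implant.

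The dates needed come from the trial, trial lead explant and implant visits, so no new data are required. The cost is a wording and programming change, one extra summary line and a somewhat smaller exposure figure.
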